PICC	Peripherally inserted central catheter

Study Aim

Currently there is little international or UK consensus regarding the route or duration of antibiotic treatment for acute osteomyelitis (OM)/septic arthritis (SA) in children. Data regarding paediatric bone and joint infections in the UK are scarce and outdated. This service evaluation will be used to:

1. Assess current case load, disease spectrum & clinical practice in the diagnosis & treatment of OM/SA in secondary & tertiary UK care
2. Determine whether a randomised controlled trial to investigate shorter duration of intravenous antibiotic therapy for bone and joint infections in children is feasible in the future.

This will be achieved in conjunction with a future component of the study (analysis plan of which not included in this document) obtaining qualitative & quantitative data on:

- a) willingness of clinicians to randomise to proposed protocol
- b) willingness of patients & parents to be randomized
- c) number of patients seen;
- d) clinical stakeholder & consumer perception of relevant outcomes

Study Design

This service evaluation is a descriptive study, examining routinely collected clinical data for all eligible paediatric cases of OM and SA presenting at participating tertiary and secondary healthcare centres over a minimum of a 6 months period.

Participating centres

All Tertiary and Secondary centres routinely treating cases of OM or SA from across England will be invited to participate in this national service evaluation. They will record data on all cases accrued over at least a 6 month period.

Participant selection criteria

All eligible patients presenting to participating centres with a diagnosis of bone and joint infection will be enrolled with no maximum, and data will be entered into a web based database.

Inclusion Criteria

All children from birth to 16 years with a clinical diagnosis of osteomyelitis or septic arthritis admitted to participating hospitals from home, or referred from another centre.

Exclusion Criteria

Patients whose parents have specifically requested for their child not to be included in the study.

Participant identification and recruitment

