Posters displayed on admitting wards notify parents and patients that the centre is participating in a national service evaluation of children's bone and joint infections. Parents will have the opportunity to inform a member of their child's care team if they do not want their child's information entered into the database.

Sample size calculations

The study is funded to enable a maximum of 1,000 cases of OM or SA to be entered into the database. In order to get an accurate national evaluation, all participating centres will be asked to record cases for at least six months. It is estimated that at least 500 cases will be accrued by around 50 centres over a 6-12 month period. All eligible cases at participating centres will be recorded.

Data Collection

We will record demographic details and details of hospitalisation(s) including transfers between hospitals; type and site of disease; routine haematology, biochemistry and microbiology; radiological procedures; surgical procedures; length of IV therapy; antimicrobials used, route and duration; reason/criteria; used for oral switch (if any); and clinical outcomes at 3 months.

These data are to be collected from the patients' clinical notes. Training will be provided for teams at participating centres. The study will use a password protected web based data collection form that can be accessed at all participating hospitals.

Study Objectives

The study has three major objectives:

1. What are the clinical, biochemical and radiological criteria used by UK paediatricians / orthopaedic surgeons / radiologists to diagnose osteomyelitis?
2. What is the range of durations of intravenous and oral antibiotics used to treat osteomyelitis? What factors affect durations (e.g. surgery / blood tests / microbiology results).
3. What are the rates of treatment failures / complications for different:
 - (a) Antibiotic regimes used at participating centres?
 - (b) Surgery types used at participating centres?

and what actions were taken following a complication at participating centres?

These objectives are broken down into further sub-objectives:

- 1A:** Describe the study sample: demographics; past medical history; presenting limbs/joints affected; and diagnosis types aiming to identify factors predisposing children to bone and joint infections. Describe pre-presentation variables that affect drug choice, dosage and duration, in particular age, allergies and co-morbidities.

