- 2C:** Describe the combinations of blood-tests carried out immediately prior to oral switch and summarise the test results. Calculate the average CRP at oral switch as a proportion CRP_{max} . Summarise blood test results over time: from presentation through to last test.
- 2D:** Describe the surgical procedures carried out post diagnosis but prior to discharge, i.e. therapeutic procedures. How many children had only one procedure, two procedures or more than two?
- 2E:** Summarise the length of time spent in hospital: from hospitalisation to discharge.
- [2F]: Summarise imaging carried out after initiation of IV, split by site type and image type. For each imaging type, identify cases that had at least one image carried out.
- 2G:** Describe the antibiotic regimes prescribed at discharge (drug, dose, frequency and duration). As part of this – what percentage went home on IV as opposed to oral?
- 2H:** Were discharge antibiotic regimes adhered to? Percentages of treatments shortened or changed post discharge, split by who made the decision: parent, hospital or GP. Describe the main reasons for non-adherence or change of regime post discharge.
- 3A:** Describe rates of different types of complication, and cross-tabulate with types of action taken.
- 3B:** Describe rates of Treatment Failure (Yes/No) and Any Complications (Yes/No) for different antibiotic regimes types. Measure associations between regime types and the two outcomes: Treatment Failure; and Any Complications.
- 3C:** Describe rates of Treatment Failure (Yes/No) and Any Complications (Yes/No) for different surgery types carried out post presentation. Measure associations between surgery types undertaken and the two outcomes: Treatment Failure; and Any Complications.

Description of the study population

Representativeness of cases accrued

The participating centres will be summarised and checked that they broadly represent all areas of the country. The numbers of cases withdrawn will be recorded.

Sample characteristics and initial categorisation of types of cases

The demographics of the sample (age, gender, medical history) will be described using summary statistics. Based on past medical history, cases will be categorised into four groups:

1. Simple cases
2. Complex cases
3. Current presentation due to infected implant or infected surgery from past orthopaedic surgery. (Subset of complex cases)
4. Misdiagnosed

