The number and percentage of types of sample for micro-biological testing (e.g. blood, pus, etc.) that are typically taken from children will be reported [see Table 1D-2].
- [1E] The number and percentage of cases with test results at presentation for: each of 6 blood tests; and the combinations ‘CRP & ESR’ and ‘CRP & no ESR’ will be reported, split by centre type (Tertiary / Secondary) [see Table 1E-1]. A boxplot for each of the six blood test measures at presentation will be created to show the distribution of results. Proportions with elevated results (above centre-specific normal ranges) will be calculated for each blood test type [see Table 1E-2].

The blood test result ‘CRP_{max}’ will be summarised for culture-positive and culture negative cases and a box plot created to compare these. This analysis will be split by age-group. This is to explore whether a higher CRP_{max} is associated with particular organisms. Differences that are clinically significant will be tested for statistical significance using appropriate hypothesis tests [see Table 1E-3].
- [1F] There are five imaging methods that could be requested by clinicians to aid diagnosis. The number and percentage of cases for each imaging type used prior to diagnosis will be reported, split by centre type (Tertiary / Secondary) and of these the number and percentage abnormal [see Table 1F-1].

Objective 2

Treatment of children with SA or OM takes the form of antibiotic treatment and additionally for some cases, surgical intervention. Initially antibiotics are given intravenously. At a later date, antibiotics are given orally – the timing of the switch is based on clinical judgement that the child has recovered sufficiently and is capable of taking drugs orally.

- [2A] The lengths of time on IV antibiotics, oral antibiotics, and total antibiotic duration will be summarised using appropriate descriptive statistics. (Note that these times are based on what happened during hospital stay and what was **planned** at discharge. It is not possible to obtain data for the actual date when antibiotics were stopped post discharge.) Results will also be split by centre type, whether there was at least one surgical procedure after initiation of IV antibiotics, if CRP_{max} occurred at presentation, and by microbes detected. [See Table 2A-1].

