Antibiotic regimes will be further summarised for the sample: Number of antibiotics given in the initial treatment; timing of oral switch (<1 wk, 1-2 wks and >2 wks)); total course of antibiotics (shortened vs standard); dose (augmented at least once vs standard dose throughout where ‘augmented at least once’ is defined as having at least one high dose of IV antibiotics); and total number of different antibiotics prescribed over the full treatment period [see Table 2A-2].

- [2B] Antibiotics prescribed during hospital stay will be summarised using frequencies and percentages. There are a large number of antibiotics that could be prescribed by either route. Of these, 4 named IV antibiotics and 5 named oral antibiotics are of particular interest. A category labelled ‘other’ will be used to define all other antibiotics given by each route. For each antibiotic and route, summary statistics will be reported for whether it was part of the initial prescription; given at least once; frequency of administration of doses during a day; daily dose per kg weight of child; and duration of course (> 1 week Y/N). This will give an overview of the most commonly prescribed antibiotics during hospital stay [see Table 2B-1].

Initial IV antibiotic prescriptions will be compared between secondary and tertiary site types; between children with and without penicillin allergy; and with and without sickle cell disease [see Table 2B-2].

- [2C] Blood test results are routinely used to aid the decision to stop giving antibiotics via IV (ie. oral switch). The combinations of blood tests carried out immediately prior to (on the day before or on the day of) the oral switch will be reported as numbers and percentages. CRP as a proportion of CRP_{max} will be summarised [see Table 2C-1].

The change in blood test results over time will be explored graphically using boxplots. For each blood test type, a plot will be produced showing the distribution of results at: presentation; initial of IV; and on each day following start of IV.

- [2D] The number and percentage of cases undergoing different types of surgery post diagnosis will be reported [see Table 2D-1].
- [2E] Appropriate summary statistics will be used to describe length of hospital stay for cases – overall, and split by age-group and centre type [see Table 2E-1].
- [2F] The number and percentage of cases with imaging after initiation of IV will be reported split by site type and image type, with results given.

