As this is a service evaluation, there should be only a small number of withdrawals. Those that do occur will be documented. It may be of importance if withdrawals are clustered by centre.

Missing data will be noted and wherever possible, the reasons reported. If a large amount of data critical to the analysis are missing, some changes to the analysis plan may be needed.

Setting results in context of previous research

Once the service evaluation has been completed the results will be set in context of the existing evidence base.

References

2. ICH E3 chapter 12.

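### Later boxes in the daily CRP plot of [2C] are likely to over-represent slow responders, so CRP may appear to fall more slowly than it does

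*SAP*

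**What the plan says.** The SAP's analysis text for [2C] under Objective 2 sets the purpose of the display: "The change in blood test results over time will be explored graphically using boxplots". For each type of blood test, "a plot will be produced showing the distribution of results at: presentation; initial of IV; and on each day following start of IV". Sub-objective 2C in Study Objectives gives the span: "Summarise blood test results over time: from presentation through to last test". Each child's series therefore ends at that child's own last result.

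The Study Design section describes the work as "examining routinely collected clinical data for all eligible paediatric cases of OM and SA", and Data Collection adds: "These data are to be collected from the patients' clinical notes". No testing schedule is stated.

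Two statements link the results to the course of treatment. Item [2C] says "Blood test results are routinely used to aid the decision to stop giving antibiotics via IV (ie. oral switch", and the introduction to Objective 2 says that "the timing of the switch is based on clinical judgement that the child has recovered sufficiently and is capable of taking drugs orally".

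The SAP names no fixed group of children for the plot, no last plotted day, no count per box and no within-child measure of change. Appendix A has no template for it. On gaps in the data, the missing-data section says only: "Missing data will be noted and wherever possible, the reasons reported".

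**The concern.** A row of daily boxes shows change over time only if the same children, or a representative share of them, appear in each box. Here the plotted variable helps decide when a child leaves IV treatment. If children are tested less, or not at all, once they have recovered, those whose CRP falls quickly drop out of the later boxes and those with high or slowly falling CRP remain. A reader following the medians would then be comparing different children on different days.

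The evaluation is meant to help judge whether a trial of shorter IV therapy is feasible. Table 2C-1 relates CRP to the child's own maximum, but only around the oral switch, so this plot is the only planned day-by-day course of CRP. A reader who takes the late boxes at face value would think that CRP stays raised for longer than it typically does.

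**Working it through.** The SAP gives no CRP level, rate of fall or testing frequency, so there is no figure of its own to reproduce. The direction follows from its text; the size can only be illustrated.

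**1. Direction.** (a) A child contributes only on days with a routine result. (b) Blood results and judged recovery inform the end of IV treatment. (c) If testing also ends or thins with recovery, the chance of appearing in the day-d box rises with CRP. (d) The median of those tested on day d is then above the median of all children. Step (c) is an inference; the SAP does not state it.

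**2. Illustration.** All inputs are assumptions from outside the SAP: starting CRP C₀ log-normal with median 80 mg/L and log-SD 0.6; halving time h log-normal with median 2 days and log-SD 0.5; CRP on day d = C₀ × 0.5^(d/h). A child is tested on day d only if the previous day's CRP was at least 20 mg/L. Simulated medians (mg/L):

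| Day | All children | Tested that day | Share tested |
|---|---|---|---|
| 1 | 54 | 55 | 99% |
| 2 | 38 | 40 | 94% |
| 3 | 26 | 32 | 81% |
| 5 | 13 | 27 | 47% |
| 7 | 7 | 25 | 24% |
| 10 | 2 | 24 | 9% |

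With a stop level of 10, the day-7 median among those tested is 16 against 7; with 30, it is about 35 against 7.

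**3. Other assumptions.** A second simulation used starting log-SD 0.8, median halving time 2.5 days and daily log-noise 0.2, with stopping possible from day 2. With halving-time log-SD 0.5, day-7 medians for all against tested children were 10.4 against 30.6 under a hard stop at 20. They were 10.4 against 37.5 when the chance of stopping rose gradually as CRP fell.

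**4. When the effect shrinks or vanishes.**
- Testing only thins (70% tested if the previous day's CRP was at least 20, otherwise 30%), with the inputs of step 2: 11 against 7 on day 7 and 3.1 against 2.4 on day 10, so no plateau.
- Stopping unrelated to CRP, with the inputs of step 3: 10.4 against 10.4 on day 7.
- No differences between children in starting CRP or halving time: 11.5 against 11.5 on day 7.

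**5. Candidate remedies.** Under step 2, the day-7 CRP as a percentage of the child's own starting value has median 22% in those tested against 9% in all children; on day 10 it is 19% against 3%. Dividing by baseline therefore leaves the selection in place. In a separate check run, a mixed model on log CRP using all of each child's results gave 5.5 mg/L on day 7 against a true 7.3, where the boxplot median was 23.6.

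**The case against.** The strongest reply is that one link is missing. The SAP does not say that testing stops, or that children go home, at the oral switch. Note (a) to Table 2A-1 counts oral treatment before discharge, sub-objective 2G asks what percentage went home on IV, and 2C runs to the last test rather than to the switch. This stands: a reader might infer that the plot is bound to show a false plateau, but the text supports only a likely distortion, and step 4 shows cases with little or none.

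A reader might also infer that the plan has no other view of how CRP resolves. It does: Table 2C-1 gives CRP at the switch as a proportion of the child's own maximum, for fast and slow switchers alike. That is one time point per child, however, and does not replace a daily course.

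Third, the study is descriptive, the plot is exploratory, and no estimate, test or design parameter is tied to it. That limits the harm to a misleading figure. It does not remove it, because the figure is offered as change over time and the SAP plans no count or caution to go with it.

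Finally, the missing-data section promises to note missing data and, where possible, reasons. It does not address results that are absent because testing stopped.

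**Conclusion.** The point holds in a limited form. The later CRP boxes in [2C] are likely to over-represent slow responders and so make the fall look slower than it is. This rests on the SAP's own statements about routine data and about what drives the switch, plus the assumption that testing ends or thins with recovery.

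The size cannot be obtained from the SAP. Across the assumed cases that link testing to CRP and let children differ, the day-7 median among tested children ran from about 1.6 times the all-children median (11.1 against 6.7, thinning only) to about five times (34.8 against 6.7, stop level 30). The distortion would be absent if stopping were independent of CRP.

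A reader might go further and conclude that none of the boxes show change over time. The illustration does not support that: on days 1 and 2 the two medians nearly coincide. Nor does the argument carry over to haemoglobin, platelets or the other tests, for which no direction has been established. The plan should be improved here, but no inference in it is overturned.

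**What to change.** Keep the boxplots and amend [2C] as follows:

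1. Under each day, print the number of children tested and the number still on IV.
2. End the plot at a day when most children still contribute, and state the rule for choosing it in advance.
3. Add one summary of change over time for CRP: either the trajectory from a mixed model on log CRP using all of each child's results, or the time to first CRP below 50% of the child's own maximum, censored at the last test if this is not seen.

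Percentage of baseline among the children tested each day should not be the replacement, because it keeps the same selection.

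The cost is SAP wording and a little programming, with no new data. The mixed model assumes that missing later values are predictable from those observed. The time-to-event version assumes that censoring at the last test is uninformative, which is open to doubt if testing stops because a child has recovered. The report should state whichever assumption applies.

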Any children not falling into any of these categories will be excluded from the analysis.

Definitions

1. Simple cases

Children presenting with SA or OM for the first time, and with no chronic comorbidities. Specifically:

- No orthopaedic surgery 6 months prior to presentation on same limb/joint
- No chronic co-morbidities (sickle cell disease, known immunocompromise, indwelling central venous catheter or PICC, cystic fibrosis, or cerebral palsy).

2. Complex cases

Children presenting with SA or OM who already have a diagnosis of SA or OM and/or have chronic comorbidities, but who are not presenting because of an infected implant from previous orthopaedic surgery. Specifically:

- Not presenting because of an infected implant
- Any orthopaedic surgery in 6 months prior to presentation on same limb/joint
- Any chronic co-morbidities (sickle cell disease, known immunocompromise, indwelling central venous catheter or PICC, cystic fibrosis, or cerebral palsy).

3. Infected implants

Children presenting with SA or OM who already have a diagnosis of SA or OM and who are presenting because of an infected implant from previous orthopaedic surgery.

4. Incorrect diagnosis of SA/OM

Some children captured by the database were treated for SA/OM but were later found to have a different diagnosis.

Completeness of follow-up

Follow-up data are collected at a follow-up visit at around 3 months post discharge. The number lost to follow up will be reported and the reasons where known will be documented. Any deaths and their causes will be reported separately.

Study Outcomes

This study examines many measurements routinely made in the diagnosis, treatment, and aftercare of children with SA or OM. There are three areas of key interest: Diagnosis (Objective 1); Treatment (Objective 2); and Complications Arising and/or Treatment Failures (Objective 3). The key endpoints are:

Diagnosis:

- Bones and joints affected
- Time taken from first presentation to:
 1. Referral to hospital
 2. Having surgery
 3. Initiation of IV antibiotics [this time-point used also as a proxy for a diagnosis being made]
- Surgical procedures carried out prior to diagnosis
- Imaging types used (X-ray, CT scan, ultrasound, bone scan, MRI), and results obtained
- Diagnostic blood tests carried out (Hb, WBC, N, Plt, CRP, ESR) and their outcomes
- Microbiological tests carried out (presence of any of 8 named micro-organisms)

Antibiotic Treatment in and post hospital stay:

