- [2G] Antibiotics prescribed at discharge will be summarised using frequencies and percentages. There are a large number of antibiotics that could be prescribed by either

route. Of these, 4 named IV antibiotics and 5 named oral antibiotics are of particular interest. A category labelled ‘other’ will be used to define all other antibiotics given by each route. For each antibiotic and route, summary statistics will be reported for whether it was given at least once; daily dose per kg weight of child; and planned duration of course. This will give an overview of the most commonly planned antibiotic regimes at discharge [see Table 2F-1].

[2H] Antibiotic regimes post discharge are not always adhered to. The number and percentage of those stopped early will be reported, split by who took the decision (Parent / Hospital / GP). In the same way the number and percentage of patients who had a change to the planned regime will be reported split by who made the change (Hospital / GP). The frequencies of 5 possible reasons for shortening or changing regime will be explored [see Table 2G-1].

Objective 3

[3A] The number and percentages of cases experiencing a complication of any kind will be reported. These will be further split by ‘Complication Type’, and cross-tabulated with ‘Action Taken’ (None / Surgery / Change of antibiotic regime / Re-admission to hospital / Other) [see Table 3A-1].

[3B] Treatment failure is determined by complications that result in certain actions. e.g. Surgery. The outcomes ‘Treatment Failure’ (Y/N) and ‘Any Complication’ (Y/N) will be cross-tabulated with three antibiotic regime variables: Timing of oral switch (Early / Standard); Total course of antibiotics (Shortened / Standard); and Overall dose (High / Normal). Associations between regime types and outcomes will be measured using odds-ratios and 95% CIs. This will give an overview of whether treatment failure and complications may be more likely for certain types of regime [see Table 3B-1].

[3C] Treatment Failure (Y/N) and Any Complication (Y/N) will be cross-tabulated with surgery undertaken (limited to surgery post presentation). Associations between surgery types and outcomes will be measured using odds-ratios and 95% CIs. This will give an overview of whether treatment failure and complications may be more likely for certain types of surgery [see Table 3C-1].

Analyses of missing data / withdrawals

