Complication type:						
Fever						
Recurrence of						
Infection						
Dislocation						
Subluxation						
Pathological						
Fracture						
Sinus						
Other						

3B: Treatment failures and complications by type of antibiotic regime.

TABLE 3B-1

Antibiotic Regime	Treatment Failure?			Any complication?		
	Yes	No	Odds ratio	Yes	No	Odds Ratio
Timing of oral switch						
Early (< 2 weeks)						
Standard / Late (> 2 wks)						
Total course of antibiotics						

Shortened (< 6 weeks)

Standard (> 6 weeks)

Dose Repeated for IV
and oral separately

High

Majority Lower range

3C: Treatment failures and complications by type of surgery.

TABLE 3C-1

Surgery	Treatment Failure?			Any complication?		
	Yes	No	Odds ratio	Yes	No	Odds Ratio
Surgery undertaken after date of 1 st presentation						
Aspiration						
Incision and drainage						
Drill decompression						
Curettage/excision						
Arthrotomy						
Arthroscopy						
Amputation						
Debridement						
Fasciotomy						
Compartment decompression						
Secondary closure						
Skin graft						
Other plastic surgery

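### In [3C] the operation that makes a child a treatment failure also counts as the surgery exposure, which pushes the failure odds ratio above 1; [3B] can be distorted the same way, but only under conditions the SAP leaves open

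*SAP*

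**What the plan says.** **Outcome.** SAP, Analysis, Objective 3, [3B]: "Treatment failure is determined by complications that result in certain actions. e.g. Surgery". Surgery is the only action named. Item [3A] lists the possible actions on a complication as "None / Surgery / Change of antibiotic regime / Re-admission to hospital / Other".

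**Surgery exposure.** Item [3C] has Treatment Failure and Any Complication "cross-tabulated with surgery undertaken (limited to surgery post presentation"). Sub-objective 3C asks for rates "for different surgery types carried out post presentation". The row label in Appendix A, Table 3C-1 opens "Surgery undertaken after date of 1" and goes on to name first presentation. All three places give a lower time limit. None gives an upper limit or leaves out surgery done for a complication.

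**Contrast within the SAP.** Surgery is bounded elsewhere. Table 1C-1 stops at the day IV antibiotics start, and sub-objective 2D reads "Describe the surgical procedures carried out post diagnosis but prior to discharge, i.e. therapeutic procedures". Item [3C] takes over neither limit.

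**Regime exposures.** Item [3B] relates the same two outcomes to timing of oral switch, total course and overall dose. For the durations, [2A] notes that "these times are based on what happened during hospital stay and what was" planned at discharge. Follow-up data come from a visit about 3 months after discharge (Completeness of follow-up). The SAP does not say whether complications during the hospital stay count as outcomes, or whether treatment during a re-admission counts as hospital stay.

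**Effect measure.** Both items use odds ratios with 95% confidence intervals, with no adjustment described.

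**The concern.** An exposure should be fixed before the outcome it is meant to explain. In [3C] one event can be both. Take a child who had no initial operation, then has a complication and is operated on for it. The operation makes the child a failure, and the same operation moves the child from the unexposed to the exposed row. Failures are thus enriched for surgery by definition, whatever the effect of the initial procedure.

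The stated purpose of Table 3C-1 is to show whether failure may be more likely after certain types of surgery. A procedure often used to deal with complications would look harmful for that reason alone. A larger sample does not help: it only narrows the interval around the wrong value.

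In [3B] the route is less direct. A complication before the oral switch may prolong IV treatment or the planned course. The child would then be classed as standard rather than early or shortened because of the complication. Early switch and short courses would look safer than they are. That matters because the Study Aim asks whether a trial of shorter IV treatment is feasible.

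**Working it through.** The SAP gives no failure rate, no share of children operated on and no expected odds ratio, so there is no figure to reproduce. The check asks what odds ratio is expected when there is no true effect. All shares below are assumptions. The comparator in [3C] is not stated and is taken to be children without the procedure in question.

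**[3C], Treatment Failure**

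- p = share of children who have the procedure as initial treatment, the same in failures and non-failures (no effect).
- q = share of failures for whom that procedure is the action on the complication.
- Exposed share among failures: p + (1 − p)q. Unexposed share: (1 − p)(1 − q).
- Odds among non-failures: p/(1 − p).
- Expected odds ratio: [p + (1 − p)q] / [p(1 − q)]. The failure rate cancels out.

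| p | q = 0 | q = 0.10 | q = 0.25 | q = 0.50 |
|---|---|---|---|---|
| 0.40 | 1.00 | 0.46/0.36 = 1.28 | 0.55/0.30 = 1.83 | 0.70/0.20 = 3.50 |
| 0.20 | 1.00 | 0.28/0.18 = 1.56 | 0.40/0.15 = 2.67 | 0.60/0.10 = 6.00 |
| 0.05 | 1.00 | 0.145/0.045 = 3.22 | 0.2875/0.0375 = 7.67 | 0.525/0.025 = 21.0 |

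The artefact grows as the procedure becomes rarer as initial treatment. It is absent (q = 0) for a procedure never used for a complication.

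**Could it look significant?** Take 500 cases (the SAP's accrual estimate for all case types; the simple cases analysed first would be fewer), an assumed 5% failure rate, p = 0.40 and q = 0.50. The expected cells are 17.5 exposed and 7.5 unexposed among 25 failures, and 190 and 285 among 475 non-failures. The odds ratio is 3.5. The standard error of its logarithm is √(1/17.5 + 1/7.5 + 1/190 + 1/285) = 0.446, so the 95% interval is 1.46 to 8.40. With q = 0.25 the interval is 0.82 to 4.12.

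**[3C], Any Complication.** The same formula applies, but q is now a share of all complications. If 25% of failures but only 10% of all complications are treated by the procedure, then at p = 0.40 the odds ratio is 1.28 instead of 1.83.

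**[3B], early against standard switch**

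- e = share switching early.
- h = share of failures who would have switched early but are moved to standard by a complication before the switch.
- Expected odds ratio: [e(1 − h)/(1 − e(1 − h))] / [e/(1 − e)].
- With e = 0.50 the divisor is 1. For h = 0, 0.10, 0.25 and 0.50 the result is 1.00, 0.45/0.55 = 0.82, 0.375/0.625 = 0.60 and 0.25/0.75 = 0.33.

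The value h = 0 is a real possibility: it holds if every complication follows discharge and re-admission treatment is not counted.

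**After the fix.** With exposure cut off before the first complication, q = 0 and h = 0, and every expected odds ratio above is 1.00.

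**The case against.** **The plan may intend something narrower.** The restriction to surgery after presentation may serve only to leave out the past operations of Table 1A-4, and complication surgery has its own column in Table 3A-1. That is plausible. But [3C], sub-objective 3C and Table 3C-1 all leave the window open, and an analyst following them would count complication surgery.

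**[3B] is not circular by construction.** A reader might infer that it is, because a change of antibiotic regime is a listed action. The documents do not support this. By the [2A] note the durations rest on the hospital stay and the discharge plan, so a change ordered after discharge does not move a child between switch or course categories. Only complications before switch or discharge can do so, or treatment in a re-admission if that is counted. This objection stands, and the [3B] point is conditional.

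**Dose.** A reader might also infer that one high dose given for a complication puts a child in the high-dose row. The rule of at least one high dose belongs to [2A] and Table 2A-2. Item [3B] speaks of overall dose, and Table 3B-1 sets high against a majority in the lower range. The ever/never argument cannot be carried into [3B], so no size is claimed for dose.

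**Not every surgery odds ratio is inflated.** This is correct: procedures never used for complications are unaffected, and Any Complication is not defined by an action.

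**The study is descriptive.** The odds ratios are offered as an overview, no decision rule depends on them, and the SAP asks only whether a trial is feasible. This lowers the weight of the point. It does not remove it, because an overview with confidence intervals will still be read as comparing procedures and regimes.

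**Conclusion.** For Treatment Failure in [3C] the point holds with high confidence. As written, outcome and exposure can be the same operation, and the odds ratio is pushed above 1 for every procedure type used to manage complications. Over the assumed shares shown, the expected value with no effect runs from 1.28 to 3.5 at 40% initial use and reaches 7.7 for a procedure with 5% initial use that is the action in a quarter of failures. The direction follows from the definitions; the size depends on shares that only the data can give. The Any Complication odds ratios are affected less.

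For [3B] confidence is moderate. Distortion is possible because exposure is not cut off at the first complication. It would make early switch and shortened courses look falsely safe, but it may be zero. A reader might conclude that the SAP's evidence on shorter treatment is biased in a known direction. That goes too far while the SAP leaves open whether in-hospital complications count.

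This should be fixed before analysis, but it does not undermine the descriptive aims of the evaluation.

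**What to change.** **[3C].** Count as exposure only procedures done before the child's first recorded complication. If complication dates are not held, limit exposure to procedures in the index admission and leave out any identifiable as an action on a complication. Show complication surgery only in Table 3A-1. The fallback is weaker, because that table has a single general surgery column; whether a given operation can be linked to a complication depends on the database. Write the rule into [3C] and the row label of Table 3C-1.

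**[3B].** Use discharge from the index admission as a landmark. Take the regime from that admission and its discharge plan, and compute the odds ratios for failures and complications first recorded after it. Tabulate in-hospital complications descriptively, and set those children aside from the odds ratios rather than counting them as event-free.

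**Cost.** A derivation rule and a few lines of SAP text. Somewhat fewer events enter the odds ratios, so intervals widen. The change removes the circularity only. Sicker children may still be more likely both to have surgery or longer treatment and to fail, and the report should say so beside Tables 3B-1 and 3C-1.
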